5.7 OTHER ANALYSES

5.7.1 Summaries of Conduct of Study

Study enrollment, duration, study drug discontinuation, and study discontinuation, as well as reasons for study drug discontinuation and study discontinuation, will be listed and summarized overall and by treatment arm. Major protocol deviations, including major deviations with regard to inclusion and exclusion criteria, will also be listed and summarized overall and by treatment arm.

5.7.2 Summaries of Treatment Group Comparability

The evaluation of treatment group comparability between the treatment arms will include summaries of demographic and baseline characteristics, including stratification factors and patient treatment history. Continuous variables will be summarized using means, standard deviations, medians and ranges. Categorical variables will be summarized by counts and proportions.

5.7.3 Pharmacokinetic Analyses

The PK objective for this study is to characterize the GDC-9545 PK profile (\pm LHRH agonist) based on Plasma concentration of GDC-9545 at specified time points. This analysis will be based on PK analysis population, which will consist of all randomized participants in the GDC-9545 arm who have at least one evaluable GDC-9545 plasma concentration. PK parameters (e.g., area under the concentration-time curve, time to maximum concentration, maximum concentration observed, and half-life if appropriate) will be estimated from an intensive PK sample-subset patient population. Summary statistics

(mean, standard deviation, coefficient of variation, median, minimum, and maximum) will be presented for PK data. Plasma GDC-9545 concentration versus time data will be tabulated and plotted.

GDC-9545 PK data may be pooled and analyzed using a population PK analysis approach as appropriate and reported in a standalone report.

5.7.4 Biomarker Analyses

The exploratory biomarker objective is based on the relationship between biomarkers in blood, plasma, and tumor tissue and efficacy, safety, PK, disease biology, or other biomarker endpoints. No formal statistical analysis of exploratory biomarkers will be performed. Data may be analyzed in the context of this study and in aggregate with data from other studies. Results may be presented in a separate report.

5.7.5 Health Status Utility

The exploratory health status utility objective for this study is to evaluate health status utility scores of patients treated with GDC-9545 compared with physician's choice of endocrine monotherapy on the basis of the EQ-5D-5L. These data will be used in pharmacoeconomic models and reported separately from the CSR.

5.7.6 Analyses of China Subpopulation

A separate analysis will be performed for the China subpopulation, where data from all participants enrolled at mainland China and/or Taiwan (i.e., during both the global enrollment phase and the extended China enrollment phase) will be combined and summarized. Results from these analyses will be summarized in a separate Clinical Study Report.

The efficacy objective of the China subpopulation analyses is to evaluate whether the efficacy of GDC-9545 compared with physician's choice of endocrine monotherapy in the China subpopulation (enrolled during both the global enrollment phase and the extended China enrollment phase) is consistent with the efficacy observed in the global population enrolled during the global enrollment phase. Therefore, no formal hypothesis testing will be performed for China subpopulation.

The China subpopulation analyses will be conducted at the same time as global population. If the PFS data in the China subpopulation is not mature at the time of primary analysis, an additional PFS analysis in the China subpopulation may be conducted. Data for the

China subpopulation will be analyzed using the same statistical methods as described in Section 5.1–5.7 when data allow.

5.8 INTERIM ANALYSES

Currently there are no interim analysis planned for primary endpoint, PFS.

5.8.1 Interim Analyses for Secondary Efficacy Endpoint: OS

The study will incorporate three OS analyses (two interim analyses and one final analysis). The first OS interim analysis will be performed at the time of the primary PFS analysis. The second OS interim analysis will be performed after the occurrence of approximately 119 deaths and is projected to occur at approximately 30 months (~12 months after Primary Analysis) after the first patient is randomized. The final OS analysis will be performed after the occurrence of approximately 149 deaths (projected to occur approximately ~40 months after the first patient is randomized). The Lan-DeMets implementation of the O'Brien and Fleming use function will be used to control the overall type I error for the OS comparison at a two-sided 0.05 significance level.

The OS analyses were designed with an overall 5% (two-sided) level of significance to detect HR ratio of 0.893, which corresponds to an improvement in median OS from 25 months to approximately 28 months. However, this study is not designed to formally test OS. For the target number of OS events and anticipated study timeline, the OS analyses will be largely underpowered, i.e. ~10% statistical power. The details of the OS analyses are shown in Table 3. The exact efficacy boundary will be updated based on the actual number of observed OS events at the time of OS analysis.

Table 3: Assumptions and Characteristics for the Interim and Final Analyses of OS

Assumption	Findings
First interim analysis of OS	
(to be performed at time of final PFS analysis)	
Estimated cutoff date ^a	18 months
Projected number of events (% of final events)	60 (20%)
Projected MDD ^b (p-value)	0.418 (< 0.0008)
Second interim analysis of OS	
Estimated cutoff date ^a	30 months
Projected number of events (% of final events)	119 (39.7%)
Projected MDD ^b (p-value)	0.661 (< 0.0242)
Final analysis of OS	
Estimated cutoff date ^a	40 months
Projected number of events (% of final events)	149 (49.7%)
Projected MDD ^b (p-value)	0.717 (< 0.0428)

HR = hazard ratio; MDD = minimally detectable difference;

^a Estimated data cutoff time from first randomization. Analysis results will be available after data cleaning.

^b The largest observed HR that is projected to be statistically significant.

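### Do the percentages of final events in SAP Table 3 make the overall survival boundaries wrong?

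*SAP*

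**What the plan says.** SAP Section 5.8.1 sets out the OS analyses: "The study will incorporate three OS analyses (two interim analyses and one final analysis". The first takes place at the primary PFS analysis and the second at about 119 deaths. For the last, "The final OS analysis will be performed after the occurrence of approximately 149 deaths". On error control, with the two-sided level set to 0.05, "The Lan-DeMets implementation of the O'Brien and Fleming use function will be used to control the overall type I error for the OS comparison". On updating, "The exact efficacy boundary will be updated based on the actual number of observed OS events at the time of OS analysis".

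Table 3 of the same section has, for each analysis, a row headed "Projected number of events (% of final events". The entries, with the projected minimal detectable difference (MDD, the largest hazard ratio that would be significant) and its p-value threshold, are:

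| OS analysis | Deaths | Printed % | MDD | p-value |
|---|---|---|---|---|
| First interim | 60 | 20% | 0.418 | 0.0008 |
| Second interim | 119 | 39.7% | 0.661 | 0.0242 |
| Final | 149 | 49.7% | 0.717 | 0.0428 |

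SAP Section 2.1 tests OS only if PFS is significant at the primary analysis. Section 5.8.1 adds that the study was not designed for a formal OS test and that power is about 10%.

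**The concern.** A final analysis cannot fall at 49.7% of its own final events, so the row contradicts the text beside it. With a spending function, the fraction of planned information determines how much alpha is available at each look. An analyst who took the row at face value would infer planned information of 300 deaths (60 divided by 0.20), would find only a sliver of the 0.05 spent by the last look, and would apply a far stricter final threshold than the one printed. OS is the only endpoint after PFS in the testing hierarchy, so its boundary should not be in doubt. The first-interim MDD of 0.418 also looks slightly too small for 60 deaths at p = 0.0008.

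**Working it through.** **Inputs.** Deaths 60, 119 and 149, two-sided alpha 0.05, Lan-DeMets O'Brien-Fleming-type spending (SAP Section 5.8.1); about 300 patients randomized 1:1 (SAP Section 3).

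**Step 1: where the printed percentages come from.**

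| Deaths | Divided by 300 | Divided by 149 |
|---|---|---|
| 60 | 20.0% | 40.3% |
| 119 | 39.7% | 79.9% |
| 149 | 49.7% | 100% |

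The printed figures match the patient denominator at all three looks. They are event-to-patient ratios under the wrong label.

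**Step 2: which fractions produced the printed boundaries.** With 0.025 in each tail, cumulative one-sided spending at information fraction t is

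α(t) = 2[1 − Φ(2.2414/√t)],

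where 2.2414 is the upper 0.0125 normal quantile. At the first look with t = 0.40, α = 0.000394, so z = 3.357 and two-sided p = 0.00079, which prints as 0.0008. Later boundaries follow by recursive numerical integration. The MDD at d deaths is exp(−2z/√d).

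| Fractions used | p-values | MDD |
|---|---|---|
| Printed in Table 3 | 0.0008 / 0.0242 / 0.0428 | 0.418 / 0.661 / 0.717 |
| 0.40 / 0.80 / 1 | 0.0008 / 0.0242 / 0.0428 | 0.420 / 0.661 / 0.718 |
| 60/149, 119/149, 1 | 0.0008 / 0.0240 / 0.0428 | 0.422 / 0.661 / 0.718 |
| 0.20 / 0.397 / 0.497 | 0.000001 / 0.0007 / 0.0027 | 0.284 / 0.539 / 0.612 |
| 0.20 / 0.397 / 1 | 0.000001 / 0.0007 / 0.0497 | 0.284 / 0.539 / 0.725 |

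Fractions of 0.40, 0.80 and 1 reproduce all three printed p-values to four decimals. The exact ratios to 149 differ only at the second look, by 0.0002. Neither set based on the printed percentages comes close. The boundaries were therefore derived with 149 deaths as full information, and the mislabelled row played no part in them.

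**Step 3: type I error.** A simulation of one million trials under the null, at fractions 60/149, 119/149 and 1 with the printed p-values as thresholds, gave an overall two-sided error of 0.0499. With thresholds built from the printed percentages it was 0.0029.

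**Step 4: first-interim MDD.** At exactly 60 deaths, p = 0.0008 gives exp(−2 × 3.3528/√60) = 0.421, against 0.418 printed. The 60 is a rounded projection. With 59.5 deaths, t = 59.5/149 = 0.3993, z = 3.3600, p = 0.00078 (prints as 0.0008) and MDD = exp(−2 × 3.3600/√59.5) = 0.4185 (0.41846, prints as 0.418). That is the edge of the rounding range, so this is a possible explanation and not a confirmed one, but it shows that the three printed figures can coexist.

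**Step 5: power.** For a hazard ratio of 0.893 and 149 deaths, |ln 0.893| × √149/2 = 0.691, and Φ(0.691 − 1.96) = 0.102. This agrees with the stated 10% and again takes 149 deaths as the final count.

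**The case for a change.** The best case for a change is that an update of the boundary needs two numbers: the observed deaths and the planned maximum. The SAP names the first but never says outright that the denominator is 149. The only figures it labels as shares of final events imply 300. An update is also likely to be needed: the Protocol's summary of this study (Section 1.2.2.2) reports OS events below 10% at the primary cutoff among 303 patients. If that means deaths per patient, it is about 30 or fewer, against 60 projected. Using 300 would move the final threshold from 0.0428 to 0.0027, about 16 times stricter, and would spend roughly 0.003 of the 0.05.

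What stands is that the label is wrong, and the arithmetic of the misuse is right. What does not stand is that the plan leads anyone there. The final analysis is fixed at about 149 deaths in the text and again in Table 3. The full 0.05 is allotted to the set of analyses that ends there, a final threshold of 0.0428 is printed beside that count, and no analysis at 300 deaths exists. A statistician who rebuilt the boundary from the percentages would fail to reproduce the table and would see why. The misuse would also make the test conservative; it could not inflate type I error.

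**Conclusion.** The row label in Table 3 is wrong, and the rest of the OS design is sound. The percentages are shares of about 300 patients; as shares of the 149 planned final deaths they are 40.3%, 79.9% and 100%. The printed p-values already correspond to 40%, 80% and 100% information and hold the two-sided error at 0.05. The updating rule uses observed deaths, so following the SAP as written gives correct boundaries. The MDD difference at the first interim (0.418 against 0.420 to 0.422) can be accounted for by rounding of a projected count.

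This rests on two assumptions: that 149 deaths is the planned full information, which the text, the printed p-values and the stated power all support, and that spending is 0.025 in each tail, which is the form that reproduces the table. The practical weight is small in any case. The SAP gives OS about 10% power and tests it only after a significant PFS result, and Protocol Section 1.2.2.2 reports PFS at p = 0.1757, so the gate to a formal OS test did not open. Relabelling the row would be tidier, but it would change no threshold, no analysis and nothing the trial can conclude.

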6. SUPPORTING DOCUMENTATION

This section is not applicable, since there is no additional supporting document. For Synopsis, Schedule of assessments, PRO forms, etc. refer to study protocol.

